### III. Study Design

#### A. Design Overview

RPT193-02 is a randomized, double-blind, dose-ranging study in adults with moderate-to-severe AD who have had an inadequate response to topical therapies or in whom topical therapies are contraindicated with a treatment duration of 16 weeks (112 days).

Approximately 268 subjects who meet eligibility criteria and consent to participate in the study are randomly assigned in a 1:1:1:1 ratio to one of four treatment groups:

- RPT193 50mg once daily
- RPT193 200mg once daily
- RPT193 400 mg once daily
- Placebo once daily

A subject is considered to have completed the study if he/she has completed all phases of the study including a 35-day maximum screening period (Week -5 to Day -1), a 16-week double-blind treatment period (Day 1 to Week 16) and an 8-week follow-up period (Week 16 to Week 24).

#### B. Study Population

##### 1. Inclusion Criteria

Adult subjects with moderate-to-severe AD are eligible to be included in the study only if all 17 criteria were met according to the protocol.

##### 2. Exclusion Criteria

Adult subjects with moderate-to-severe AD are excluded from the study if any of the 35 criteria were met according to the protocol.

#### C. Sample Size Predictions

- [Redacted]
- [Redacted]
- [Redacted]
- [Redacted]

Based on the assumptions above and using a two-sample t-test, a sample size of 60 subjects per treatment group is needed to detect the treatment effect on the primary endpoint between RPT193 and placebo. Assuming a 10% drop out rate, a total sample size of 268 subjects (67 per treatment group) will be needed.

## D. Treatment Randomization

In all parts of the study, randomization will occur prior to first dosing, at the Day 1 visit. Approximately 268 subjects will be randomized 1:1:1:1 to one of 4 groups (3 dose levels of RPT193 or placebo). In total and accounting for a dropout rate of 10%, approximately 60 subjects are anticipated to complete the study in each group.

A randomization list will be generated using validated software. The randomization list will be kept secured until the study blind is broken at the end of study.

The randomization list is stratified based on baseline vIGA scores (vIGA of 3 vs. 4) and prior dupilumab or tralokinumab use (yes or no). The list is uploaded into an Interactive Web Response System (IWRS) and the Investigator or designee will be able to acquire a randomization number for eligible subjects by connecting to the IWRS.

## E. Assessment Schedule

Refer to Appendix 1 for the schedule of assessments.

# IV. General Analytical Considerations

## A. Data Sources

All information requested in this protocol will be recorded on the electronic Case Report Forms (eCRFs) or external source (or via other data collection methods, eg, electronic laboratory data transfer or patient questionnaire data).

## B. Definitions

### Baseline

Unless otherwise specified, Baseline is defined as the last non-missing assessment prior or equal to the date and time of the first administration of study treatment. In the case where the last non-missing assessment and the first administration of study drug coincide and time of measurement is not available, that measurement will be considered Baseline unless the assessment was scheduled to be post-dose in the protocol.

### Change from baseline/Week 16

Change from baseline is defined as the post-baseline value minus the baseline value, unless specified otherwise. Percent change from baseline =  $(\text{Change from Baseline}/\text{Baseline}) \times 100$ .

Change from Week 16 is defined as the post-baseline value minus the Week 16 value, unless specified otherwise. Percent change from Week 16 =  $(\text{Change from Week 16}/\text{Week 16}) \times 100$ .

### Study Day 1

Study day 1 is defined as the date of randomization for untreated randomized subjects, or the date of first administration of study treatment for treated subjects.

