2.0 INTRODUCTION

2.1 Study Rationale

RPT193-02 is designed to assess the efficacy and safety of multiple dose levels of RPT193 in subjects with moderate-to-severe atopic dermatitis (AD). This randomized, double-blind, placebo-controlled study will compare 3 dose levels of RPT193 to placebo with a treatment duration of 16 weeks. Investigational product will be administered as monotherapy for AD in adult subjects who have had an inadequate response to topical medications for AD (e.g., corticosteroids) or who are otherwise unable to take topical medications. Maximum clinical benefit in the 4-week Phase 1b trial was observed 2 weeks after cessation of treatment and suggested that RPT193 may have therapeutic effects beyond the dosing period. Thus, after completion of treatment at 16 weeks, subjects will continue to be followed for an additional 8 weeks to understand whether further improvement in clinical parameters and/or sustained responses are observed beyond the treatment period.

The data generated during the current study will contribute to efficient and appropriate design of future clinical studies, including pivotal studies with RPT193 in subjects with AD.

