
 
Explore the durability of the treatment effect after cessation of treatment at Week 16.
 
	
 
% change in EASI at Weeks 18, 20, and 24 compared to Week 16 among those not receiving rescue therapy from Week 8 to Week 16.
 
% change in SCORAD at Weeks 18, 20, and 24 compared to Week 16 among those not receiving rescue therapy from Week 8 to Week 16.
 

Exploratory (Pharmacokinetic)	

 
To evaluate the PK of RPT193 following administration of multiple oral doses of RPT193 administered orally QD for 16 weeks to subjects with moderate-to-severe AD.
 
	
 
PK parameters at Week 2, 4, 8, 12, 16, and 18.
 

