### A. Efficacy Assessments

#### 1. Eczema Area Severity Index (EASI)

The EASI is a clinician assessment that is collected at Screening/ Visit 1, Baseline/ Visit 2, Visit 3/ Week 2, Visit 4/ Week 4, Visit 5/ Week 8, Visit 6/ Week 12, Visit 7/ Week 16, Visit 8/ Week 18, Week 9/ Week 20 and Visit 10/ Week 24 using the e-Diary.

The EASI is a composite score ranging from 0 to 72 that takes into account the degree of erythema, induration/infiltration (papules), excoriation, and lichenification (each scored as =None, 1=Mild, 2=Moderate 3=Sever) for each of 4 body regions (head and neck, trunk, upper extremities and lower extremities), with adjustment for the percentage of BSA (assessed by the palmar method) involved for each body region ( 0= 0%, 1=1-9%, 2=10-29%, 3=30-29%, 4= 50-69%, 5=70-89%, 6=90-100%) and for the proportion of the body region to the whole body (.1 for head and neck, .3 for trunk, .2 for upper extremities and .4 for lower extremities)

The domain score will be calculated in the ADaM dataset when all assessments are completed. The following is the calculation for each body region:

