## E. Exploratory Efficacy Analysis

All exploratory efficacy analysis will be based on the FAS. Descriptive summary statistics will be provided by treatment and visit for exploratory endpoints listed below. No imputation will be utilized for missing data.

- Percent change in SCORAD from baseline at Week 2, 4, 8, 12, and 16
- Percent change in BSA from baseline at Week 2, 4, 8, 12, and 16
- Change from baseline to Week 16 in sleep loss from the SCORAD VAS
- Change from baseline to Week 16 in POEM
- Change from baseline to Week 16 in DLQI
- Change from baseline to Week 16 in Skin pain NRS
- Change from baseline to Week 16 in PtGA  
A shift table from baseline will be provided.
- Change from baseline to Week 16 in ADSS  
For item 1 and 3 a shift table will be provided to display the change from baseline. The change from baseline for item 2 will be presented descriptively.

- Change from baseline to Week 16 in ACQ-5  
A shift table from baseline will be provided for each question
- Percent of subjects achieving a PtGA score of 0 or 1 and a  $\geq 2$  point reduction from baseline at Week 2, 4, 8, 12, and 16. The assessment at each specific timepoint will be independently considered.
- Subgroup analysis of the primary efficacy endpoint as outlined in section IV.I
- Proportion of subjects maintaining responder status at Weeks 18, 20, 24 among those achieving the corresponding responder status at Week 16 and not receiving rescue therapy from Week 8 to Week of interest. The endpoint at Week 20 will not consider Week 18 status and will include subjects that do not use rescue from Week 8 to Week 20. Similarly, Week 24 will not consider responder status at Week 18 and Week 20 and will only include subjects that did not use rescue from Week 8 to Week 24. An additional analysis will be conducted without consideration of the use of rescue medication after Week 16. The following responder status will be analyzed separately.
  - EASI-50
  - EASI-70
  - EASI-90
  - vIGA score of 0 or 1
- Percent change in EASI at Weeks 18, 20, and 24 compared to Week 16 among those not receiving rescue therapy from Week 8 to Week of interest. In other words, the analysis at Week 20 will only include subjects who do not use rescue from Week 8 to Week 20.
- Percent change in SCORAD at Weeks 18, 20, and 24 compared to Week 16 among those not receiving rescue therapy from Week 8 to week of interest.

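### The only continuous durability endpoints divide by the Week 16 score, so for EASI they are undefined at 0 and inflated near 0; absolute change from Week 16 and percent change from baseline should lead instead

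*SAP*

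**What the plan says.** Protocol 2.1 gives the purpose of the 8-week follow-up: to learn "whether further improvement in clinical parameters and/or sustained responses are observed beyond the treatment period". One of the two exploratory durability objectives (Protocol 3.0, Table 1; SAP II) is worded "Explore the durability of the treatment effect after cessation of treatment at Week 16". It has two endpoints, which SAP VI.E carries into the analysis:

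- "Percent change in EASI at Weeks 18, 20, and 24 compared to Week 16 among those not receiving rescue therapy"
- "Percent change in SCORAD at Weeks 18, 20, and 24 compared to Week 16 among those not receiving rescue therapy"

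SAP IV.B supplies the formula. It first defines the simple difference: "Change from Week 16 is defined as the post-baseline value minus the Week 16 value, unless specified otherwise". It then defines "Percent change from Week 16" as that difference divided by the Week 16 value, times 100. It gives no rule for a Week 16 value of zero, and no durability endpoint uses the simple difference.

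On the scale itself, SAP VI.A.1 states: "The EASI is a composite score ranging from 0 to 72". Inclusion criterion 6 (Protocol 5.1) requires an EASI of at least 16 at baseline; nothing bounds the Week 16 score from below. No imputation is planned for follow-up (SAP IV.D.2) or for exploratory endpoints (SAP VI.E). Continuous data are summarized by n, mean, SD, minimum, median and maximum (SAP IV.J).

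**The concern.** Percent change from baseline is safe here because eligibility puts a floor under the denominator. Percent change from Week 16 has no such floor, and its denominator is itself a treatment outcome. A subject who has cleared has no value, even if the disease later returns. A subject who has almost cleared can contribute a very large percentage for a clinically small change. Both kinds of subject should be more common in an effective arm, and keeping only non-rescued subjects probably makes low Week 16 scores more common still.

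At stake is the only continuous description of what happens across non-rescued subjects after dosing stops. The protocol says the data will inform later studies, so a distorted picture of relapse could mislead design decisions even though nothing is formally tested.

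**Working it through.** The plan gives no expected value for this metric, so there is no stated figure to reproduce. The check applies the IV.B formula to attainable EASI scores, then shows the effect on an arm and between arms.

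**1. Attainable scores.** With whole-step grading, the smallest non-zero EASI under SAP VI.A.1 is one sign at grade 1, involvement score 1, in the head and neck region: 1 × 1 × 0.1 = 0.1. Zero is also attainable.

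**2. Single subjects.** Percent change from Week 16 = (later − Week 16) / Week 16 × 100. Baselines are assumed: 16 for the first four rows, 25 for the last two.

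| Week 16 | Later | Absolute change | % change from Week 16 | % change from baseline, Week 16 then later |
|---|---|---|---|---|
| 0 | 0.8 | +0.8 | undefined | −100 then −95 |
| 0.4 | 1.2 | +0.8 | +200 | −97.5 then −92.5 |
| 1.6 | 2.4 | +0.8 | +50 | −90 then −85 |
| 8 | 8.8 | +0.8 | +10 | −50 then −45 |
| 20 | 20.8 | +0.8 | +4 | −20 then −16.8 |
| 20 | 30 | +10 | +50 | −20 then +20 |

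A 0.8-point rise in a subject still 85% better than baseline scores the same +50% as a 10-point flare from 20 to 30.

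**3. One subject in an arm.** Let all subjects but one go from 10 to 10.5 (+5%) and one go from 0.1 to 0.8 (+700%).

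- n = 40: (39 × 5 + 700) / 40 = 22.4%
- n = 50: (49 × 5 + 700) / 50 = 18.9%
- n = 60: (59 × 5 + 700) / 60 = 16.6%

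The median stays at 5.0% each time. The mean absolute change at n = 50 is (49 × 0.5 + 0.7) / 50 = 0.504 points, so the one subject barely matters.

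**4. Stability within an arm.** Assumed: 60 subjects, baseline EASI uniform on 16 to 45, Week 16 a Beta(0.9, 1.1) fraction of baseline, later change with mean +1 and SD 3, and 0 to 10% additional cleared subjects. Across simulated arms:

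- the mean percent change centred on 31 to 32%, with a 95% range of about 4% to 146%;
- the median percent change was about 7% (0 to 16%);
- the mean absolute change was 1.1 points (0.3 to 1.9);
- subjects at or below a tenth of their baseline supplied about 57% of the summed absolute percent change;
- with 5 to 10% additional cleared, about 3 to 6 of 60 had no value.

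**5. Comparison between arms.** Assumed: baseline uniform on 16 to 45; improvement at Week 16 normal with SD 30%, capped at 100%; scores rounded to 0.1 and not below 0; the same later-change distribution in every arm (mean +1.0, SD 2.5). Only the mean improvement at Week 16 varies.

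| Mean improvement | Undefined | Mean % change from Week 16 | Median | Mean absolute change |
|---|---|---|---|---|
| 30% | 1.0% | +8.3% | +4.7% | 1.01 |
| 40% | 2.3% | +11.3% | +5.3% | 1.02 |
| 55% | 6.7% | +18.9% | +6.7% | 1.06 |
| 65% | 12.3% | +26.3% | +7.9% | 1.10 |

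Arms with almost the same worsening in points differ about threefold on the mean, and the better arm looks worse. The median leans the same way, less strongly. Absolute change drifts slightly because a score cannot fall below 0.

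**The case against.** Much of the case on the other side stands.

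- A reader might infer that durability is measured only this way. It is not. A second exploratory objective follows the proportion of Week 16 responders who keep an EASI response or a vIGA of 0 or 1 at Weeks 18, 20 and 24. Those endpoints do not divide by the Week 16 score, keep cleared subjects in, and speak directly to sustained response. They are binary and restricted to responders, however, so they cannot show the size of further gain or loss across all non-rescued subjects.
- A reader might infer that cleared subjects vanish unseen. SAP IV.J requires n and the maximum, and composite EASI scores are listed by subject, so a reduced n would show. It would not separate a zero denominator from a missed visit.
- The median is already planned and resists the outliers. It does not restore the cleared subjects.
- A reader might extend the EASI figures to SCORAD. The documents do not support that: a SCORAD of 0 needs zero extent, zero on all six signs including dryness, and no itch or sleep loss.
- A reader might take the simulated sizes as forecasts. The documents give no Week 16 distribution. The 6.7% undefined is simply the capped tail, P(Z > (100 − 55)/30 = 1.5), and the +18.9% depends on rounding: without it one run gave +117%, and excluding scores below 1.0 gave about +11 to 12%. That fragility supports the point about the mean but rules out quoting any one size.
- Percent change from Week 16 is an endpoint in the protocol, so removing it would depart from the protocol. Adding to it is the simpler course.

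**Conclusion.** The concern holds for EASI, within limits. Applied as written, the formula gives no value at a Week 16 score of 0 and very large values near 0. The mean is then unstable, and an arm with better Week 16 responses can appear to relapse more. The undefined and inflated values follow from the formula alone. The size, such as mean percent changes of +8% to +26% for arms worsening by 1.0 to 1.1 points, rests on assumed distributions and on rounding to 0.1.

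SCORAD is less affected and the responder-maintenance endpoints are unaffected. It would be tempting to say that the trial's efficacy findings are compromised, but the documents do not support that: these endpoints are exploratory, summarized descriptively and outside the testing sequence, so no primary or key secondary conclusion changes. This is a worthwhile, low-cost improvement to the only continuous measure of its objective.

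**What to change.** In SAP IV.B and VI.E:

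1. Add absolute change from Week 16 at Weeks 18, 20 and 24, and percent change from original baseline at Weeks 16, 18, 20 and 24, as the main continuous durability summaries for EASI and SCORAD. Compute them for every non-rescued subject with observed scores at both visits. A zero at Week 16 then excludes nobody; missing visits and rescue still do.
2. Keep the protocol-specified percent change from Week 16 as supportive, interpreted by its median. State that it is not calculated when the Week 16 score is 0, and report the number of such subjects per arm.
3. Record the addition in SAP I.C.

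The cost is a few extra summary tables and a documented SAP addition; no new data are needed. SAP I.B allows modification until treatment unblinding. Because SAP IV.F gives a limited sponsor group unblinded Week 16 efficacy results before follow-up ends, the addition should be dated before that analysis.

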### Study Day

Study day is calculated relative to date of Day 1 as following:

- Study Day = (date of event – date of first dose) + 1 if the date of the event is on or after the randomization date or date of first dose.
- Study Day = (date of event – date of first dose) if the date of the event is prior to the randomization date or date of first dose.

### C. Analysis Windows

Efficacy assessments that are collected at scheduled visits as defined in the protocol will be analyzed according to their windowed visits defined by actual study day. Unscheduled visits will not be used in the analysis if a scheduled visit is available and the scheduled visits fall into their corresponding analysis windows. Unscheduled visit will be used in the analysis only if the scheduled visit is not available or none of the scheduled visits are fall into the corresponding analysis windows.

If more than one assessment occurs within a single visit window, then the analysis will take the one closest to the target day. If assessments are equidistance to the target day, then earliest assessment will be selected.

The following efficacy visit windows will apply to all efficacy data except for PP-NRS, Pain NRs or ADSS:

Visit	Week	Target Study Day	Efficacy Assessment Windows (Inclusive)
2	Baseline	1*	-35 to 1
3	Week 2	15	2 to 21
4	Week 4	29	22 to 42
5	Week 8	57	43 to 70
6	Week 12	85	71 to 98
7	Week 16	113	99 to 119
8	Week 18	127	120 to 133
9	Week 20	141	134 to 154
10	Week 24	169	155 to 172

\*Note: Day of last non-missing assessment prior or equal to the date and time of the first administration of study treatment

PP-NRS, Pain NRS and ADSS are collected daily throughout the study. These efficacy endpoints will be analyzed according to their windowed weekly assessments defined by actual study day.

For the continuous assessments of PP-NRS, Pain NRS, and ADSS item 2, if there are at least three non-missing results collected within the weekly analysis window, the average of these assessments will be used for the analysis. Otherwise, the assessment will be considered missing.

For the categorical ADSS item 1 and 3, if there are at least three results collected within the weekly analysis window, the worst assessment within the weekly analysis window will be used for analysis purposes. The worst assessment will be order from best to worst as 0 (“not at all”) to 4 (“very difficult”). Otherwise, the assessment will be considered missing.

The following weekly efficacy visit window will be applied for PP-NRS, Pain NRS and ADSS:

Weekly Analysis Visit	Efficacy Assessment Windows (Inclusive)
Baseline	1*
Week 1	2 to 8
Week 2	9 to 15
Week 3	16 to 22
Week 4	23 to 29
Week 5	30 to 36
Week 6	37 to 43
Week 7	44 to 50
Week 8	51 to 57
Week 9	58 to 64
Week 10	65 to 71
Week 11	72 to 78
Week 12	79 to 85
Week 13	86 to 92
Week 14	93 to 99
Week 15	100 to 106
Week 16	107 to 113
Week 17	114 to 120
Week 18	121 to 127
Week 19	128 to 134
Week 20	135 to 141
Week 21	142 to 148
Week 22	149 to 155
Week 23	156 to 162
Week 24	163 to 169

\*Note: Day of last non-missing assessment prior or equal to the date and time of the first administration of study treatment

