- Fasting required for labs at Baseline, Day 113 (Week 16), and Day 127/ET/Discon (Week 18). A subject should refrain from eating or drinking (except for water) for a period of at least 8 hours prior to the lab draw.
- FSH at Screening only for females of non-childbearing potential.
- The ACQ-5 instrument will only be assessed in subjects reporting a history of ongoing asthma at Screening.

- h. 
- i. Photographs will be taken at the selected sites. One or more most affected body regions, per Investigator's judgement, may be photographed.
- j. The e-Diary will be dispensed to the subject or the e-Diary application will be loaded to the subject's device at Baseline. Collection or removal of application will occur at EOS or at ET/Discon. Subjects enter e-Diary information on a daily basis for their compliance with study treatment starting Baseline/Day 1, recording daily pruritus, daily skin pain NRS, and ADSS starting at Baseline/Day 1.
- k. On Day 1, Day 15, Day 29, Day 57, and Day 85, the study drug will be administered at the study center after all other assessments are performed. All other daily drug intake will be self-administered by the subject, at home, at approximately the same time of the day through Day 112.
- l. PK blood sampling will be done pre-dose on Day 1, Day 15, Day 29 and Day 57.
- m. Tape stripping is only required for subjects in the US and Canada; tape stripping should not be performed for subjects in Poland. Tape strips will be collected from lesional and non-lesional skin pre-dose at Baseline. Tape strip samples will also be collected at the same sites sampled at Baseline on Day 29, Day 57, Day 113, and on Days 141 and 169, if applicable.
- n. Two skin microbiome samples will be collected at Baseline, one from lesional and one non-lesion skin. A skin microbiome sample will also be collected at subsequent visits at the same lesional site sampled at Baseline.
- o. Plasma blood sampling will be done pre-dose.
- p. The immunophenotyping sample is only required for subjects in the US and Canada; immunophenotyping samples should not be collected from subjects in Poland.
- q. Blood sample will be collected from subjects who have consented to participate in the genetic analysis component of the study. Participation is optional. Please see [Section 8.7](#) for further details.

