### B. Subject Characteristics

Demographics and baseline disease characteristics will be summarized by treatment group based on the Safety Analysis Set.

- Subgroups as outlines in section I. Subgroups
- Age at time of consent (years)
- Childbearing potential of female subject (Yes, No including reasons)
- Baseline weight (kg)
- Baseline height (cm)
- Baseline BMI (kg/m^2)
- Race (American Indian or Alaska Native, Asian, Black or African American, Native Hawaiian or Other Pacific Islander, White, Other)
- Ethnicity (Hispanic or Latino, Not Hispanic or Latino, Not Reported)
- Fitzpatrick skin type (Type I, II, III, IV, V and VI)
- Subjects with prior history of dupilumab experience (Yes, No)
- Subjects with prior history of tralokinumab experience (Yes, No)
- Subjects with prior history of dupilumab or tralokinumab experience (Yes, No)
- Subjects with prior history of JAK inhibitor (Yes, No)
- Baseline Pruritus Numerical Rating Scale
- Baseline Skin Pain Numerical Rating Scale
- Baseline Patient Global Assessment (0=Clear, 1=Almost Clear, 2=Mild, 3=Moderate, 4=Severe)
- Baseline Total Dermatology Quality of Life Index
- Baseline Total Patient-Oriented Eczema Measure
- Baseline Atopic Dermatitis Sleep Scale
  - Item 1: Difficulty Falling Asleep (0=Not at all, 1=A little bit, 2= Somewhat, 3=Quite a bit, 4=Very difficult)
  - Item 2: Number of Night-time awakenings
  - Item 3: Difficulty to get back to sleep last night (0=Not at all, 1=A little bit, 2= Somewhat, 3=Quite a bit, 4=Very difficult)
- Baseline Total Asthma Control Questionnaire
- Baseline Total SINO-Nasal Outcome Test

- Baseline Eczema Activity and Severity Index
  - Baseline Validated Investigator Global Assessment
  - Baseline Body Surface Area BSA Affected
  - Baseline Total SCORing Atopic Dermatitis
  - Atopic dermatitis disease duration (years)
  - Atopic comorbidities (food allergy, allergic rhinitis, or asthma) (Yes or No)
- All demographics and baseline disease characteristics will be provided in subject listings.

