#### **5. Atopic Dermatitis Sleep Scale (ADSS)**

The ADSS will be recorded daily by the subject in an e-Diary.

The three-item ADSS captures the self-reported impact of itch on sleep disturbance each day, including: difficulty falling asleep (Item 1); number of night-time awakenings (Item 2), and difficulty falling back asleep after waking (Item 3) during the previous night. Each ADSS item is scored individually. For items 1 and 3, subjects will be asked to select a score ranging from 0 ("not at all") to 4 ("very difficult"). For item 2, subjects will select the number of times they woke up each night, ranging from 0 to 29 times. Subjects are only to answer item 3 if their answer to item 2 is greater than 0.

The daily and average/worst weekly scores for the individual items of the ADSS results will be presented in a data listing.

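### ADSS items 1 and 3 set one Day 1 entry against the worst of 3–7 Week 16 entries, item 3 goes missing when subjects largely stop waking, and the SAP drops secondary models without recording it (minor)

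*SAP*

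**What the plan says.** **ADSS, items 1 and 3.** The e-Diary starts on Day 1: Protocol 1.3, footnote j, has subjects "recording daily pruritus, daily skin pain NRS, and ADSS starting at Baseline/Day 1". The weekly window table in SAP IV.C sets baseline at Day 1, defined as "Day of last non-missing assessment prior or equal to the date and time of the first administration of study treatment". Week 16 is Days 107–113. For items 1 and 3 the weekly value exists "if there are at least three results collected within the weekly analysis window"; then "the worst assessment within the weekly analysis window will be used for analysis purposes", and otherwise the week is missing. Item 2, PP-NRS and skin pain use the weekly average instead. SAP VI.E states: "For item 1 and 3 a shift table will be provided to display the change from baseline". Exploratory endpoints are descriptive and not imputed.

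**Item 3.** SAP VI.A.5 and Protocol 8.1.14 share a skip rule: "Subjects are only to answer item 3 if their answer to item 2 is greater than 0". SAP V.B lists "Item 3: Difficulty to get back to sleep last night" with categories 0 to 4 and none for a night without waking. For item 2, SAP VI.E says: "The change from baseline for item 2 will be presented descriptively".

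**Other secondary endpoints.** Protocol 9.4.2.1 gives continuous secondary endpoints the primary ANCOVA and binary ones a logistic model, with no restriction to the key secondaries. SAP VI.D.2 makes the other continuous and binary secondary endpoints descriptive. SAP I.C records two changes from the Protocol: removal of the region stratum, and transfer of the CCL17/CCL22 subgroups to another plan.

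**The concern.** The expected maximum of several entries exceeds the expected value of one entry whenever scores vary from night to night. The shift table therefore mixes real change with a difference in how the two time points are summarised. A subject with stable scores, or already at 4 on Day 1, is not affected; others tend to move to 'worse'. A reader could take the wrong direction from an arm's table.

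For item 3, whether a value exists depends on the outcome. Subjects who largely stop waking leave the table at Week 16, and those who slept through the night before Day 1 have no baseline. If the drug changes awakenings, the loss differs by arm.

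On the secondary endpoints, a reader cannot tell whether the models were dropped on purpose or overlooked.

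**Working it through.** The documents state no figure for any of this. ADSS variability and waking rates below are assumptions, shown as ranges.

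**Step 1. Entries compared.** Recording starts on Day 1, so baseline is one entry. The Week 16 window holds 113 − 107 + 1 = 7 days, so the weekly value is the worst of 3 to 7 entries. Applying the three-result rule to a one-day baseline would make every baseline missing, so the single-entry reading is the only workable one.

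**Step 2. Size with no true change.** For k independent entries without ties, P(worst of k > one entry) = k/(k+1): 3/4 = 75% for k = 3, 7/8 = 87.5% for k = 7. Ties on a 0–4 scale and correlation within subject lower this. Simulated integer scores with between-subject SD 0.9, mean 1.5, 2.0 or 2.5, nightly SD 0.4, 0.7 or 1.0, and within-week autocorrelation 0 or 0.5 (3 × 3 × 2 = 18 scenarios) give:

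| Week 16 entries | 'Worse' | 'Better' |
|---|---|---|
| worst of 7 | 44–74% | 2–9% |
| worst of 3 | 34–58% | 7–17% |

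One entry against one entry is balanced. With nightly SD 1.0 and seven entries, an arm that truly improved by 1 point still shows 36–43% 'worse' and 21–29% 'better'.

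**Step 3. Between arms.** True 1-point effect, seven entries, gap in percent 'better' (points):

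| Placebo / drug change | Worst | Median | Larger gap |
|---|---|---|---|
| 0 / −1 | 17–47 | 27–65 | median, 18 of 18 |
| −0.5 / −1.5 | 24–62 | 22–47 | worst in most |
| −1 / −2 | 26–48 | 11–23 | worst, 18 of 18 |

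The sign depends on how much placebo moves, because the median reaches the floor of 0 sooner. In the first row the mean difference is largely kept: −0.72 to −0.97 with worst, −0.81 to −0.97 with the median.

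**Step 4. Item 3 missing.** With nightly waking probability p and a full diary, P(missing) = P(Binomial(7, p) ≤ 2) = (1−p)⁷ + 7p(1−p)⁶ + 21p²(1−p)⁵. At p = 0.5 this is (1 + 7 + 21)/128 = 22.7%. At 80% diary completion, p becomes 0.8p. Both time points are present with probability p × (1 − P(missing)), taking the same p on Day 1.

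| p | Missing, full diary | Missing, 80% diary | Both present, full diary |
|---|---|---|---|
| 0.7 | 2.9% | 14.0% | 68.0% |
| 0.5 | 22.7% | 42.0% | 38.7% |
| 0.3 | 64.7% | 77.7% | 10.6% |

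Arms at p = 0.5 and p = 0.3 would differ by 64.7 − 22.7 = 42.0 points in the share missing; arms with equal waking would not differ.

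**Step 5. Secondary endpoints.** SAP VI.D.2 lists one continuous endpoint (absolute PP-NRS change at Week 16) and six binary endpoints at five visits, 6 × 5 = 30 analyses. EASI-75 at Week 16 has a model as a key secondary endpoint, which leaves 29 binary analyses without one. Log-rank tests remain for time to EASI and PP-NRS response.

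**The case against.** The strongest reply is that worst-in-week is a stated rule, identical in every arm, for one of many untested exploratory endpoints. SAP VI.E asks only for a shift table; percent 'better' is a reader's summary of it. This stands, and it is why the point is minor. It does not remove the within-arm bias, which is what a shift from baseline displays.

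A reader might infer that the rule understates the drug's effect. The documents do not support that. Step 3 shows the gap shrinking only when placebo hardly changes, and placebo improvement is plausible: in the Phase 1b study 22.2% of placebo subjects with baseline itch of at least 4 had a 4-point itch response at Day 29 (Protocol 2.2.2.6).

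On item 3, a night without waking makes the question inapplicable, and item 2 records the number of awakenings. SAP IV.J by default takes percentages over the analysis population and reports n, and the table shells, which are not in these documents, may carry a not-applicable row. All fair; but subjects without a value are still not shown as improved, and no written rule separates 'no awakening' from a missed diary.

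On the secondary endpoints, the practical loss is small. Entry requires vIGA of at least 3, so every vIGA 0/1 responder also has a 2-point reduction; the two endpoints differ only for a move from 4 to 2. Percent change in PP-NRS keeps its ANCOVA and MMRM. The SAP governs the analysis, but SAP I.C exists to record such changes and is silent here.

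**Conclusion.** The point holds in three limited parts, and its severity is minor.

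1. The shift tables for ADSS items 1 and 3 are biased toward 'worse' within each arm. The direction follows from the rule wherever scores vary from night to night. The size (44–74% 'worse' with no true change and seven entries) rests on assumed score distributions. The effect on the between-arm gap has no fixed sign.
2. Item 3 availability depends on waking. The binomial figures are exact for the assumed waking probabilities, taking nights as independent. A difference between arms arises only if waking or diary completion differs.
3. Protocol 9.4.2.1 and SAP VI.D.2 disagree, and SAP I.C does not say so. This rests on the text alone.

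It would be wrong to infer that the trial's main conclusions are at risk: the primary EASI test, its dose sequence and the key secondary models use none of these rules.

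**What to change.** Make these changes in the SAP before any unblinding, which on SAP IV.F means before the Week 16 efficacy analysis.

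**(a) Items 1 and 3.** Use a Week 16 summary comparable with one Day 1 entry. One choice is the weekly median; with an even count, take whichever of the two middle values was recorded later, comparing the most recent entry of each if several nights share a value. This keeps 'worse' minus 'better' within 2.4 points in unchanged subjects for 3–7 entries; always taking the lower or upper middle value brings back 6–19 points. The other choice is the single entry closest to Day 113, which is also free of drift but noisier. State the downside: if both arms improve, the floor at 0 can make the between-arm gap in percent 'better' smaller than with 'worst'. The worst-of-week table may stay as a supplementary display.

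**(b) Item 3.** Count nights with item 2 answered toward the three-entry minimum. Show 'no awakening' as its own category at Day 1 and Week 16, without ranking it below 0. For weeks with some awakenings, summarise the answered item 3 entries and report how many there were. At 80% diary completion, weeks failing the minimum fall to P(Binomial(7, 0.8) ≤ 2) = 0.5%.

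**(c) Secondary endpoints.** Either add the Week 16 ANCOVA of absolute PP-NRS change and the logistic models for the binary endpoints, labelled nominal, or list the departure and its reason in SAP I.C. If models are added, name the imputation for vIGA: SAP VI.B assigns MI (MAR), but SAP IV.D.2 describes that method only for EASI and PP-NRS. The control-based vIGA datasets already planned would serve.

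**Cost.** SAP wording and two table shells, plus either one entry in SAP I.C or six Week 16 models (one continuous and five binary), which give 6 × 3 = 18 further unadjusted p-values. No new data and no protocol amendment.
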